4 ANALYSIS SETS/POPULATIONS

4.1 FULL ANALYSIS SET

Inclusion criteria

Patients must meet all of the following inclusion criteria to be eligible for inclusion in the study:

1. *≥ 18 year old female*
2. *HR+/HER2- breast cancer diagnosis with confirmed metastatic or advanced disease*
3. *Diagnosed with ABC/MBC between 01 January 2016 and 01 July 2021*
4. *Treatment with CDK4/6 inhibitor*

Exclusion criteria

Patients meeting any of the following will not be included in the study:

1. *Patient does not have ABC/MBC*
2. *Patient has indicated HR- or HER2+ status*
3. *Patient received a CDK4/6i as part of a clinical trial*

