4.4 SUBGROUPS

Subgroup analyses for the primary and secondary objectives will be conducted in patients who are potentially pre-menopausal, where possible. Patients who are 50 years old or younger and are on a LHRH antagonist will be included in this subgroup. Subgroup analyses will be descriptive in nature and will depend on adequate sample size.

The secondary objective will include the following subgroups for specified analyses, where possible:

[figure not shown]
- Pre-CDK subgroup is defined as ABC/MBC patients starting systemic therapy before the introduction of CDK 4/6 inhibitor (January 2016 to May 2016).
- Post-CDK subgroup is defined as ABC/MBC patients starting systemic therapy after the introduction of CDK 4/6 inhibitor (January 2019 to May 2019).

CCI

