Describing pre- and post-CDK treatment patterns and sequencing in ABC/MBC patients is one of the secondary objectives of this study. To explore treatment patterns and sequencing before the introduction of CDK4/6 inhibitor (“pre-CDK” subgroup), ABC/MBC patients diagnosed and starting systemic therapy before the introduction of Palbociclib in Canada (i.e. January 2016 to May 2016) will be investigated. To explore treatment patterns and sequencing after introduction of CDK4/6 inhibitors, a similar length of time (i.e. January – May) will be investigated; however, this will be done in 2019 to allow for sufficient time for education and uptake of CDK4/6 inhibitor usage in

PFIZER CONFIDENTIAL

[figure not shown]
clinical practice (“post-CDK” subgroup). The above dates are the time periods we propose based on clinical relevance, but they are contingent upon clinician input and review of primary objective results and are subject to change.

Treatment patterns for systemic therapy for the pre-CDK subgroup and post-CDK subgroup will be described. Sequencing of therapies received after CDK treatment will be described. Continuous and categorical variables will be described using methods outlined in Section 7.1 of this document. Bar charts may also be used to illustrate changes in treatment patterns over time if appropriate. The above-mentioned analyses will use the following or similar R packages: ‘tables’ and ‘ggplot’.

Type	Supports Protocol Objective Number	Endpoint	Population	Statistical Method/Test	Covariates used	Method of adjustment for missing values	Role of the analysis related to study objectives
Table	2	Not applicable	-Pre-CDK subgroup -Post-CDK subgroup	Descriptive stats Comparisons tests (e.g. t-test, ANOVA, Wilcoxon, Fischer)	Systemic therapies	Missing data will be summarized in table. Missing days from dates will be handled as per section 6 of this document.	To describe treatment patterns pre and post CDK.
Bar chart	2	Not applicable	-Pre-CDK subgroup -Post-CDK subgroup	Descriptive stats	Systemic therapies	Missing data will be excluded. Missing days from dates will be handled as per section 6 of this document.	To illustrate treatment patterns over time.

Time to event analysis:

PFIZER CONFIDENTIAL

CCI

Numbers

at risk and cumulative incidence will be reported for each curve. **CCI**

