	Line 1	Line 2	Line 3	Line 1	Line 2	Line 3
Chemotherapy N, Mean Tx duration (SD)						
Chemo type 1, n (%)						
Chemo type 2, n (%)						
...						
Targeted therapy N, Mean Tx duration (SD)						
Targeted type 1, n (%)						
Targeted type 2, n (%)						
...						
...						

^a Defined as treatment started between January 2016-May 2016^b Defined as treatment started between January 2019- May 2019

Table 8: Sequencing of therapies after CDK 4/6 inhibitor

[figure not shown]
	Overall (N=)
Post-CDK received in L1	
Medicinal product name 1, n (%)	
Medicinal product name 2, n (%)	
...	
Post-CDK received in L2	
Medicinal product name 1, n (%)	
Medicinal product name 2, n (%)	
...	
Post-CDK received in L3	
Medicinal product name 1, n (%)	
Medicinal product name 2, n (%)	
...	

Bar charts

Figure 5: Classes of treatments over time in all patients. Please refer to Figure.1 for reference as to how bar charts will look. Similar plots will be created for all lines of therapy.

PFIZER CONFIDENTIAL

Time to event analyses in all patients:

Figure 6: TTNT1 in all patients by type of treatment

Figure 7: TTNT2 in all patients by type of treatment

Figure 8: TTC in all patients by type of treatment

Figure 9: Overall Survival in all patients by type of treatment

Table 9: Length of Line 1 treatment in short term vs long term responders

Variables	Short term responders (n=) ^a	Long term responders (n=) ^b
Chemotherapy N, Mean Tx duration (SD)		
Chemo type 1		
N		
Mean (SD)		
Median		
Q1,Q3		
Minimum-Maximum		
Chemo type 2		
N		
Mean (SD)		
Median		
Q1,Q3		
Minimum-Maximum		
...		
Targeted therapy N, Mean Tx duration (SD)		
Targeted type 1		
N		
Mean (SD)		
Median		
Q1,Q3		
Minimum-Maximum		
Targeted type 2		
N		
Mean (SD)		
Median		
Q1,Q3		
Minimum-Maximum		
...		

^a Defined as those who are on first line therapy for up to 3 to 6 months

^b Defined as those who are on first line therapy for more than 6 months

Time to event analyses in pre-menopausal patients:

Figure 10: TTNT1 in patients who are potentially in pre-menopause by type of treatment

Figure 11: TTNT2 in patients who are potentially in pre-menopause by type of treatment

Figure 12: TTC in patients who are potentially in pre-menopause by type of treatment

Figure 13: Overall Survival in patients who are potentially in pre-menopause by type of treatment

Table 10: Length of Line 1 treatment in short term vs long term responders in pre-menopausal patients^a

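### The pre- and post-CDK groups are defined by therapy start in SAP 4.4 but by diagnosis and therapy start in SAP 7.2; read literally, 4.4 lets only the 2019 group include previously diagnosed later-line patients

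*SAP*

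**What the plan says.** SAP 4.4 defines the two groups in matching terms. The earlier one reads "Pre-CDK subgroup is defined as ABC/MBC patients starting systemic therapy before the introduction of CDK 4/6 inhibitor (January 2016 to May 2016") and the later one "Post-CDK subgroup is defined as ABC/MBC patients starting systemic therapy after the introduction of CDK 4/6 inhibitor (January 2019 to May 2019"). Neither names a line of therapy or a diagnosis date. The footnotes to Tables 4 and 7 follow this rule: "Defined as treatment started between January 2016-May 2016" for the pre-CDK columns and "Defined as treatment started between January 2019- May 2019" for the post-CDK columns. Table 7 has Line 1, Line 2 and Line 3 columns for each group.

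SAP 7.2 words the earlier group differently: "ABC/MBC patients diagnosed and starting systemic therapy before the introduction of Palbociclib in Canada (i.e. January 2016 to May 2016) will be investigated". For the later group it takes a window of similar length and says "this will be done in 2019 to allow for sufficient time for education and uptake". It does not repeat the diagnosis condition.

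Two other provisions bear on this. SAP 4.1 limits eligibility to patients "Diagnosed with ABC/MBC between 01 January 2016 and 01 July 2021", and SAP 4.3 applies the full analysis set to the secondary objective. The diagnosis limit therefore governs both groups.

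**The concern.** The secondary objective sets treatment patterns and sequencing before the introduction of CDK4/6 inhibitors beside those afterwards. For that contrast to be readable, patients should enter both groups at the same point in their disease.

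The 2016 window opens on the first eligible diagnosis date, so everyone in it is newly diagnosed. The 2019 window opens three years later. If a start in any line counts, that window also admits people diagnosed in 2016-2018 who are moving to line 2 or 3. The groups would then differ in line mix and time since diagnosis because of the calendar, and a change in pattern could be mistaken for an effect of the new drug class.

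The SAP also leaves a programmer without an answer to a simple case: does a patient diagnosed in 2017 who starts line 2 in March 2019 belong to the post-CDK group? SAP 4.4 suggests yes; SAP 7.2, read by parallel, suggests no.

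**Working it through.** The documents give no calculation for these groups, so there is no planned figure to reproduce. The first and last steps below use only the documents' dates. The second and third need assumptions.

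**1. Diagnosis time available before each window**

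- 2016: 01 January 2016 to 01 January 2016 = 0 months.
- 2019: 01 January 2016 to 01 January 2019 = 36 months.
- Longest possible time from diagnosis to a qualifying start: 151 days in 2016 (01 January to 31 May 2016) and 1,246 days in 2019 (01 January 2016 to 31 May 2019).

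**2. How many patients this could involve (illustrative)**

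Inputs:
- N = 54. Protocol section 5 and SAP section 1 expect less than 30% of 180, and 0.30 × 180 = 54, so this is a ceiling.
- Diagnoses spread evenly over the 66 months from 01 January 2016 to 01 July 2021 (assumption).
- Median line durations (assumption). The progression-free survival medians in Protocol section 7 stand in: 24.8 or 14.5 months for line 1, and 9.2 or 3.8 for line 2. The pair 10 and 5 is a pure sensitivity value.

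By hand:
- Newly diagnosed per window: 54 × 5/66 = 4.1.
- Diagnosed before the 2019 window: 54 × 36/66 = 29.5.
- Of these, starting a new line in five months with median 24.8: 29.5 × (1 − 2^(−5/24.8)) = 3.8. Share of the group: 3.8/(3.8 + 4.1) = 48%.
- With median 9.2: 29.5 × (1 − 2^(−5/9.2)) = 9.2. Share: 9.2/(9.2 + 4.1) = 69%. This is an upper value, because it applies a median seen after progression on endocrine therapy to the whole pool.

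A simulation that keeps line 1 and line 2 durations separate (exponential, one month from diagnosis to line 1, no deaths or dropout) gives, at N = 54:

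| Medians, line 1 / line 2 (months) | 2016 group | of which previously diagnosed, line 2-3 | 2019 group | of which previously diagnosed, line 2-3 | Share in 2019 |
|---|---|---|---|---|---|
| 24.8 / 9.2 | 3.24 | 0 | 7.89 | 3.96 | 50% |
| 14.5 / 9.2 | 3.23 | 0 | 9.07 | 5.18 | 57% |
| 14.5 / 3.8 | 3.25 | 0 | 8.98 | 5.06 | 56% |
| 10 / 5 | 3.24 | 0 | 9.62 | 5.79 | 60% |

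Later-line starts of any kind in the 2016 window number only 0.17 to 0.41, all in patients diagnosed inside the window.

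**3. Sensitivity to deaths**

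Protocol section 7 cites 22% five-year survival for stage IV disease. If this applied at a constant hazard, h = −ln(0.22)/60 = 0.0252 per month. The fraction of the earlier-diagnosed pool alive in January 2019 would be (1 − e^(−36h))/(36h) = 0.66. The hand-calculated shares fall to 2.5/(2.5 + 4.1) = 38% and 6.1/(6.1 + 4.1) = 60%. Survival in HR+/HER2- disease may be better than this, so the step shows sensitivity only.

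**4. If Table 7 follows a first-line cohort forward**

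Data end on 01 October 2021. Starts in January-May 2016 have about 69 down to 64 months of available follow-up. Starts in January-May 2019 have about 33 down to 28.

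**The case against.** The strongest reply is that starting systemic therapy may simply mean starting first-line treatment for advanced disease. On that reading, previously diagnosed later-line patients drop out of both groups. The Table 7 layout is compatible with it: a cohort entered at line 1 and followed into lines 2 and 3 fits a table about sequencing, whereas counting any-line starts in the window leaves the pre-CDK later-line columns almost empty. This has force, and it is why the point is that the 2019 group can contain such patients, not that it will. It does not settle the matter. The SAP writes first line where it means it (the responder definitions and Figure 20), and Table 12, laid out like Table 7, counts treatments started by date and line. The first-line reading also brings the unequal follow-up shown above.

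A reader might infer that SAP 4.4 and 7.2 yield different cohorts in both years. They do not. The diagnosis condition is explicit only for 2016, where the eligibility date makes it nearly redundant. The conflict matters for 2019, where 7.2 is silent and the condition is inferred.

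A reader might also infer that the whole comparison is confounded. Table 7 separates lines, so later-line starters do not enter its Line 1 columns. Only patients diagnosed just before January 2019 who start line 1 in the window create a small imbalance there.

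Finally, the analysis is descriptive, depends on sample size, and has provisional dates. That limits the consequences, but the clause in 7.2 allowing change concerns the dates, not the diagnosis or line condition. A descriptive contrast can still mislead if its groups are assembled differently.

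**Conclusion.** The inconsistency is real and should be resolved before the tables are programmed. What is certain is the date arithmetic: 0 months of eligible diagnosis time precede the 2016 window and 36 months precede the 2019 window. Harm to group composition requires the any-line reading, which the text permits but does not state. On that reading the effect falls on Table 4, unstratified displays and the Line 2 and 3 columns of Table 7. On the first-line reading the later-line columns are still not like for like, because follow-up differs by about 36 months.

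It would go too far to conclude that a majority of the post-CDK group will be previously diagnosed patients. The figure of roughly half rests on N = 54 as a ceiling, progression-free survival medians standing in for line durations, uniform accrual, no deaths, and every line end leading to a new line. It amounts to about 4 to 6 patients in the simulation and shows only that the effect need not be negligible.

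**What to change.** Use one rule in SAP 4.4, SAP 7.2 and the footnotes to Tables 4 and 7, stated for both years: ABC/MBC diagnosis and first-line start both within the window. Report lines 2 and 3 over the same length of follow-up from first-line start in both groups. With data ending on 01 October 2021, about 28 months is the longest period available to every 2019 starter.

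No new data are needed. The cost is SAP wording and a smaller post-CDK group: about 3 to 4 patients per window if N is about 54 (3.2 with a one-month delay from diagnosis to treatment, 4.1 with none). Spread over three lines and several drugs, such numbers may support little more than a listing, and the SAP already makes subgroups conditional on adequate size.

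The change does not remove a separate limit. The full analysis set requires treatment with a CDK4/6 inhibitor, so the pre-CDK group holds only patients who received one at some point. That should be stated beside the results.

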5 ENDPOINTS AND COVARIATES

5.1 EFFICACY/EFFECTIVENESS ENDPOINT(S)

PFIZER CONFIDENTIAL

- CCI
- [REDACTED]
- [REDACTED]

5.2 SAFETY ENDPOINTS

Not applicable.

5.3 SAFETY ENDPOINTS

Not applicable.

CCI

[REDACTED]

5.5 ENDPOINTS

Variable	Role	Data source(s)	Operational definition
Patient demographics	Baseline characteristic, potential confounder, subgroup identifier	Patient EHR	
• Date of birth• Sex• Date of death
Clinical characteristics	Baseline characteristic, potential confounder, subgroup identifier	Patient EHR	
• Date of ABC/MBC diagnosis• Age at ABC/MBC diagnosis (years)• ECOG performance score at index date (0, 1, 2, 3, 4)• ESAS• Date of last follow-up• Organ level metastatic sites (bone, brain, lungs, liver; number of sites)• Tumour stage at initial breast cancer diagnosis (I, II, III, IV, Unknown)• Tumour grade

PFIZER CONFIDENTIAL

			
 • Tumour histology • ER and PR receptor status (Positive, Negative, Unknown) • HER2 status (Positive, Negative, Unknown) • Concomitant LHRH agonists
Comorbidities	Baseline characteristic, potential confounder, subgroup identifier	Patient EHR	
 • Atrial fibrillation • Hypertension • Coronary Artery Disease/Myocardial infarction/Angina • Diabetes Mellitus • Stroke
Treatments	Exposure	Patient EHR	
 • Systemic Therapies (therapy start and stop date including combination therapies, and line of therapy) • Surgeries • Radiation Treatment
Clinical outcomes	Outcome	Patient EHR	
 • TTNT1 • TTNT2 • TTC • Overall Survival (landmark 3y)

ECOG, Eastern Cooperative Oncology Group; EHR, Electronic Health Record; ER, Estrogen Receptor; ESAS, Edmonton Symptom Assessment System; HER2, Human Epidermal Receptor Growth Factor 2; LHRH, Luteinizing Hormone-Releasing Hormone; PR, Progesterone Receptor; TTC, time from date of ABC/MBC diagnosis to starting chemotherapy; TTNT1, length of treatment for the first line; TTNT2, length of treatment for the second line

6 HANDLING OF MISSING VALUES

For categorical variables, the number of missing responses will be shown as a separate category in the analysis. For continuous variables, the number of non-missing observations will be presented. Limited use of imputation methods will be used for missing dates. For instance, if the month and year are present for a date, then “15” would be input as the date to create a complete observation. Excluding dates, no other imputation methods will be used for missing or incomplete data.

PFIZER CONFIDENTIAL

7 STATISTICAL METHODOLOGY AND STATISTICAL ANALYSES

7.1 STATISTICAL METHODS

The following analyses are expected to be conducted in R.

Analyses for continuous Data

Continuous variables will be described by the number of patients with valid/non-missing observations using mean, standard deviation (SD), quantiles (Q1, median, Q3), minimum and maximum.

Analyses for Categorical Data

Categorical variables will be described by frequencies and related percentages.

Analyses for time to event end points.

Time to event variables will be analyzed using Kaplan-Meier curves (TTNT1, TTNT2, TTC, OS). Numbers at risk and cumulative incidence will be reported for each curve.

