Understanding the effectiveness of new treatments in a diverse clinical practice as a complement to randomized clinical trial (RCT) data is important as this provides evidence of the clinical benefit of these treatments in a more heterogeneous population with comorbid conditions and variations in care delivery seen in routine clinical practice. Real-world outcomes for patients with ABC/MBC who were treated with palbociclib in combination with an aromatase inhibitor (AI) or fulvestrant have been reported in several publications and at medical congresses. A comparative effectiveness analysis of palbociclib + letrozole versus letrozole alone was presented at the San Antonio Breast Cancer Symposium (SABCS) 2019 congress and subsequently published. Using the Flatiron Health Analytics Database, a total of 1,430 female patients with HR+/HER2-MBC in the first-line setting were included in the analysis demonstrating an adjusted HR for PFS of 0.58 (95% confidence interval(CI), 0.49-0.69; $P < 0.0001$), and an adjusted HR for OS of 0.66 (95% CI, 0.53-0.82; $P = 0.0002$) (9). From a Canadian perspective, another study reported on the Ibrance® Real World Insights Study (IRIS) involving medical chart review of 247 patients with ABC/MBC treated with palbociclib in combination with either AI (n=212) or fulvestrant (n=33) (10). The 12-month progression-free rate was 90.3% for patients treated with palbociclib + AI and the 6-month progression free survival rate was 91% for those treated with palbociclib + fulvestrant. The 12-month survival rates were 95.6% for palbociclib + AI and 100% for palbociclib + fulvestrant (10).

Palbociclib has been used in Canada since its initial approval by Health Canada in 2016, and there remains a need to better understand treatment patterns and outcomes in practice for Canadian patients with a longer follow-up. Real world data is necessary to understand these

trends and subsequent clinical outcomes to inform future treatment decisions in the HR+/HER-ABC/MBC population.

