9.7. Data analysis

Detailed methodology for summary and statistical analyses of data collected in this study will be documented in a statistical analysis plan (SAP), which will be dated, filed and maintained by the sponsor. The SAP may modify the plans outlined in the protocol; any major modifications of primary endpoint definitions or their analyses would be reflected in a protocol amendment. Statistical analyses will be performed by PPD. The data will be analyzed using R (version and packages will be detailed in final SAP).

Descriptive analyses will be performed to summarize patients' baseline characteristics and outcomes of interest across the study cohort. Continuous variables will be described by the number of patients with valid/non-missing observations using mean, standard deviation (SD), minimum, maximum and quantiles (Q1, median, Q3). Categorical variables will be described by frequencies and related percentages. Number of missing observations will be reported for all variables. Time to event will be described using unadjusted Kaplan-Meier chart that will visually estimate the distribution of times to some events (i.e. progression), and will take into account those patients for which the event has not as yet occurred. Numbers at risk, cumulative incidence and survival medians will be reported for each curve. Endpoint definitions and how patients are censored for each endpoint will be further described in the SAP. Visualizations may be used to further describe treatment patterns, patient journeys, and other outcomes of interests if appropriate. The above planned data analyses are descriptive in nature and all subject to modification based on sample size and final data specifications. No inferential statistical analyses will be conducted.

PFIZER CONFIDENTIAL

Missing data will be excluded on a case by case basis and will not be imputed. This will mean that each table will not necessarily be based on the same number of patients.

CCI

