1 AMENDMENTS FROM PREVIOUS VERSION(S)

Amendment number	Date	SAP section(s) changed	Summary of amendment(s)	Reason
Version 2.0	2023-02-16	Title page	Change of protocol version identifier from "version 1.0" to "version 2.0" and the date from "2021-11-22" to "2023-01-24" and the author from PPD	SAP information has been updated. Change of staff at PPD
Version 2.0	2023-02-16	2.2 STUDY OBJECTIVES and 5.1 EFFICACY AND ENDPOINT(S) and 7.2 STATISTICAL ANALYSES	Change of "Secondary objective" with the deletion of "To evaluate efficacy of current treatment for Canadian breast cancer patients using surrogates for time to next treatment in the real-world setting including: 
• The length of treatment for the first line (TTNT1), the length of treatment for the second line (TTNT2), the time from cyclin-dependent kinase 4 and 6 (CDK4/6) inhibitor to starting chemotherapy (TTC) and overall survival (OS)• The length of treatment for short term versus long term responders" which is now included with the exact similar wording to the CCI section, except for the following wording "...the time from cyclin-dependent kinase 4 and 6 (CDK4/6) inhibitor to starting chemotherapy (TTC)..." which was replaced by "...the time from the date of ABC/MBC diagnosis to starting chemotherapy (TTC)..." in addition.	The secondary objective was adapted as the initial planned sample size (e.g., 180 patients) will be dramatically lower than expected (less than 30% of initial sample size); consequently, CCI As per clinical expert insight, the definition of TTC was clarified to the time from the date of ABC/MBC diagnosis to starting chemotherapy

PFIZER CONFIDENTIAL

Amendment number	Date	SAP section(s) changed	Summary of amendment(s)	Reason
			
“...last known activity” was replaced by “date of last follow-up or death”
 
These updates have been made throughout the document.
	

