7.2.2 Summary of all Analyses

Outcome	Analysis Set	Supports Protocol Objective Number	Subgroup	Statistical Method	Strata	Missing Data
Baseline Characteristics	All patients	1	None	Descriptive Stats	None	Missing data will be summarized in table. Missing days from dates will be handled as per section 6 of this document.
Treatment patterns	- All patients who have received Palbociclib combination treatment.	1	Pre-menopausal patients ^a	Descriptive stats, Bar charts, Sankey Diagram	None	Missing data will be summarized in table and excluded from figures. Missing days from dates will be handled as per section 6 of this document.
Treatment patterns and sequencing pre and post CDK	- All patients	2	-Pre-CDK subgroup	Descriptive stats,	None	Missing data will be summarized in table. Missing

PFIZER CONFIDENTIAL

			-Post-CDK subgroup	Bar charts,		days from dates will be handled as per section 6 of this document.
Treatment duration (TTNT1/TTNT2)	- All patients	Exploratory	Premenop ausal patients ^a	KM Curve	Systemic therapies	Missing data will be excluded. Missing days from dates will be handled as per section 6 of this document.
Time to chemotherapy (TTC)	- All patients	Exploratory	Premenop ausal patients ^a	KM Curve	Systemic therapies	Missing data will be excluded. Missing days from dates will be handled as per section 6 of this document.
Overall Survival	- All patients	Exploratory	Premenop ausal patients ^a	KM Curve	Systemic therapies	Missing data will be excluded. Missing days from dates will be handled as per section 6 of this document.
Impact of COVID-19	- All patients	Exploratory	- Patients diagnosed one year before and within first year of the pandemic	Descriptive Stats, KM Curve, Bar charts, Sankey Diagram	None	Missing data will be excluded. Missing days from dates will be handled as per section 6 of this document.

^a Patients who are potentially pre-menopausal are included in this subgroup. Please refer to section 4.4 of this document for further details about how this group is defined.

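### TTC is given only a Kaplan-Meier curve with a promised cumulative incidence, although death before chemotherapy is a competing event; a competing-risk estimate should be reported instead

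*SAP*

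**What the plan says.** SAP 7.1 puts four endpoints under one method: "Time to event variables will be analyzed using Kaplan-Meier curves (TTNT1, TTNT2, TTC, OS"). It continues: "Numbers at risk and cumulative incidence will be reported for each curve". The visible part of the time-to-event text in SAP 7.2 repeats that promise. Protocol 9.7 adds medians: "Numbers at risk, cumulative incidence and survival medians will be reported for each curve". In SAP 7.2.2 the TTC row is exploratory, is stratified by systemic therapy, and has a Kaplan-Meier curve as its only method.

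The footnote to the variable table in SAP 5.5 gives the endpoint: "TTC, time from date of ABC/MBC diagnosis to starting chemotherapy". Death is not part of that event.

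On censoring, Protocol 9.7 defers to the SAP: "Endpoint definitions and how patients are censored for each endpoint will be further described in the SAP". The SAP text where this would be expected is blacked out: the bullets of 5.1, a block after 5.3, and much of the time-to-event part of 7.2. No text is visible under Appendix heading A1.2, which is reserved for further endpoint definitions. The SAP amendment log records that a reference to last known activity became "date of last follow-up or death", without naming an endpoint. Neither document mentions competing risks in its visible text.

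**The concern.** Protocol 9.7 describes the Kaplan-Meier curve as allowing for patients whose event has not yet happened. A patient who died without chemotherapy is not waiting for it. Treating that patient as censored gives the remaining patients' future chemotherapy starts to someone who cannot have one. One minus Kaplan-Meier then describes uptake in a hypothetical population without death, and it is not a cumulative incidence.

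Two outputs would be affected: the proportion who have started chemotherapy by a given time, and any median TTC. TTC is also to be plotted by type of treatment (SAP Figures 8 and 12). The overstatement grows with mortality before chemotherapy, so treatment groups with the same chemotherapy hazard but different mortality would show the same curve although different proportions start chemotherapy. In a descriptive study these estimates are the product.

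**Working it through.** **Plan's own figure.** The documents give no TTC incidence, median or event count, so there is nothing to reproduce. The check asks how far the candidate estimands lie apart.

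**Model (assumed).** Constant hazards per year: c for starting chemotherapy, d for death before chemotherapy.

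- Death censored: 1 − KM(t) = 1 − exp(−c·t)
- Death competing (the Aalen-Johansen target): CIF(t) = c/(c+d) × [1 − exp(−(c+d)·t)]
- Death counted as an event: 1 − exp(−(c+d)·t)

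**Inputs.**

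- c = 0.20 is assumed; 0.10 and 0.35 are run as alternatives.
- Low d: Protocol section 7 reports "The 12-month survival rates were 95.6% for palbociclib + AI". So d = −ln(0.956) = 0.045.
- High d: Protocol section 7 gives 22% 5-year survival in stage IV disease. So d = −ln(0.22)/5 = 0.303. This includes deaths after chemotherapy and is not limited to HR+/HER2− disease, so it is best read as an upper bound.
- d = 0.10 and 0.15 are assumed intermediate values.

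**Example, 3 years, c = 0.20, d = 0.045.** 1 − KM = 1 − exp(−0.60) = 45.1%. CIF = 0.20/0.245 × [1 − exp(−0.735)] = 42.5%. Chemotherapy or death = 1 − exp(−0.735) = 52.0%.

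**Results for c = 0.20** (gaps in points, from unrounded values):

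| d per year | 1 − KM, 3 y | CIF, 3 y | Gap | Chemotherapy or death, 3 y | 1 − KM, 5 y | CIF, 5 y | Gap |
|---|---|---|---|---|---|---|---|
| 0.045 | 45.1% | 42.5% | 2.6 | 52.0% | 63.2% | 57.7% | 5.6 |
| 0.10 | 45.1% | 39.6% | 5.6 | 59.3% | 63.2% | 51.8% | 11.4 |
| 0.15 | 45.1% | 37.1% | 8.0 | 65.0% | 63.2% | 47.2% | 16.0 |
| 0.303 | 45.1% | 31.0% | 14.1 | 77.9% | 63.2% | 36.6% | 26.7 |

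Over all three values of c, the gap is 1.6 to 19.0 points at 3 years and 3.8 to 31.1 points at 5 years.

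**Strata.** Two treatment groups with c = 0.20 and d of 0.045 and 0.15 would both show 45.1% at 3 years. Their actual incidences would be 42.5% and 37.1%.

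**Median.** With death censored and c = 0.20, the median is ln 2/0.20 = 3.5 years. With d = 0.15, the CIF reaches 50% when 1 − exp(−0.35·t) = 0.50 × 0.35/0.20 = 0.875, so t = ln 8/0.35 = 5.9 years. That is beyond the longest possible follow-up of 5.75 years (01 January 2016 to 01 October 2021). With d = 0.303 the CIF never exceeds 0.20/0.503 = 39.8%, so there is no median.

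**Small-sample check.** The SAP amendment log expects under 30% of 180 patients: 0.30 × 180 = 54. In 4000 simulated cohorts of 54, with uniform entry over 5.5 years, a cut at 5.75 years and c = 0.20, mean 3-year 1 − KM against Aalen-Johansen was 45.2% vs 42.6%, 44.9% vs 39.4%, 45.3% vs 37.2% and 45.3% vs 31.0% for the four values of d. One minus Kaplan-Meier was never the lower of the two in any cohort.

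**The case against.** **The censoring rule is not visible.** A reader might infer from the amendment log that death is censored for TTC. The documents do not support that as fact. The phrase names no endpoint, does not say whether death is an event or a censoring date, and fits OS just as well. The redacted text may contain a clear rule. This stands, and the point is therefore conditional. It does not remove the problem: under either usual handling of death, a Kaplan-Meier curve does not give the incidence of starting chemotherapy. If the hidden rule counts death as an event, the curve is a legitimate chemotherapy-free survival curve, but it is not TTC as SAP 5.5 defines it.

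**Cumulative incidence may mean event counts.** The shells for Figures 16, 17 and 20 show cumulative events under the curve, and counts are not inflated by censoring deaths. Those shells are for TTNT1 and OS; the TTC shells visible to us (Figures 8 and 12) are titles only. This is possible, but counts would not correct the plotted curve or a median read from it.

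**The gap may be small.** At the 95.6% survival figure it is 2.6 points at 3 years with c = 0.20. Protocol section 7 also cites 100% 12-month survival with palbociclib plus fulvestrant (n=33); with no deaths the two estimates coincide. With 54 patients, no censoring and 50% incidence, the 95% half-width is 1.96 × √(0.25/54) = 13 points, larger than most of the 3-year gaps above. This limits the severity. It does not make the estimator right, since the error always runs in one direction.

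**No test depends on it.** TTC is exploratory and no hypothesis is tested. This also stands.

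**Conclusion.** The point holds in conditional form, at low severity. The visible plan promises a cumulative incidence for TTC and names only Kaplan-Meier to produce it. If death is censored, the proportion starting chemotherapy by a given time is overstated. If death is an event, the quantity is chemotherapy or death: 52% to 78% at 3 years for c = 0.20.

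The direction under censoring is certain: one minus Kaplan-Meier cannot be below Aalen-Johansen, and exceeds it once a chemotherapy start follows an earlier death without chemotherapy. The size is not fixed by the documents. At 3 years it is 45% against 42.5% down to 31%, given constant hazards, an assumed c of 0.20 per year, and death hazards taken from two survival figures that count all deaths.

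Three stronger readings go too far:

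- That the plan overstates how many patients ever reach chemotherapy. Data end on 01 October 2021, so only incidence by a given time is at issue.
- That a large bias has been shown. The upper end needs the general stage IV survival figure.
- That TTNT1 and TTNT2 share the fault. The visible text defines both as length of treatment, and their event rules are redacted.

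OS is unaffected, and so are the primary and secondary objectives.

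**What to change.** In SAP 7.1, the time-to-event part of 7.2, and the TTC row of 7.2.2:

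- State how death before chemotherapy is handled for TTC.
- Report the Aalen-Johansen cumulative incidence of chemotherapy start, with death without chemotherapy as a competing event, overall and by treatment type. Give the incidence of death without chemotherapy beside it.
- Take any median TTC from that curve, as the time when incidence reaches 50%, or report it as not reached.
- If a Kaplan-Meier curve is kept, count death as an event and label it chemotherapy-free survival. Do not label one minus Kaplan-Meier as cumulative incidence.
- State whether cumulative incidence under each curve means an estimated proportion or an event count.
- Apply the same approach to TTNT1 and TTNT2 only if their event is starting the next line. Leave OS as Kaplan-Meier.

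The cost is a few sentences in the SAP and a different R call. Date of death is already in the extraction list, so no new data are needed. Protocol 9.7 lets the SAP modify the planned analyses and calls for an amendment only for major changes to the primary endpoint, so on its terms a SAP revision is enough.
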